14.1 Adverse events

PTSD Adverse Events are defined as a \geq 10 point rise in the self-report PCL-5 since the previous therapy session or a 15 point rise from baseline or the maximum score of 80 being reached and/or relapse into alcohol and/or substance misuse at a hazardous level which integrated with the clinical judgement of the treating therapist will determine the action taken.

Self-harm adverse events are defined as responding 1 or above on the PHQ-9, question 9 and

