8.10.2 Comparison intervention

Participants randomised to the waiting list control (WL) group can continue with any ongoing care or newly engage with usual care pathways available in NHS veterans' services and charities for non-PTSD mental health concerns. Participants will be offered FIRST therapy following the completion of data collection at 20 weeks post randomisation. They will be informed of the appointment date/time for FIRST therapy commencement at the point of randomisation. Safety data is collected at six and 12 weeks and our well-performing feasibility study safety protocol will ensure that any escalation of symptoms in waiting list participants will be detected and recorded as

an adverse event (Appendix 1).

9 Phase 1: Proof of concept study

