14.3 Care escalation procedures

If the participant is in therapy, Inspire will hold responsibility and clinical governance accountability for the participant's mental health and wellbeing, including their own safety and where relevant the safety of others and including the safeguarding of children and vulnerable adults. If at point of referral or during the course of treatment, Inspire therapists become concerned about the welfare of any participant or immediate family member they will escalate their concerns through Inspire's standardised risk assessment, escalation, management and safeguarding policies and procedures. Where necessary they will contact the participant's GP to mobilise referral to crisis response, NHS primary or secondary care. Likewise, if a safeguarding and vulnerable adults concern is identified this will be escalated, acted on and reported to the relevant statutory body – safeguarding team.

Before the participant is referred to Inspire and after discharge, the participant's GP holds responsibility and accountability for the participant's mental health and wellbeing and this includes their safety. If the participant scores on the PCL-5 indicate an adverse event, the unmasked researcher responsible for participant safety will make contact with the participant within six hours of noting the rise in score and encourage them to contact their GP and/or case worker. They will advise the participant that they will need to contact the participants GP and/or case worker to alert them to the rise in PTSD symptoms. The research team will review all incoming follow-up PCL-5 and PHQ-9 scores within 72 hours of receipt.

All AE will be recorded and reported to the study PI within 72 hours and will be discussed at the biweekly research core-team sub-group meeting. A report will be included in the TSC reporting for review.

A Serious Adverse Event that occurs following discharge from Inspire but whilst in the trial will be investigated by one of the study's senior investigators (i.e. [name] or [name]) using Inspire's SAE investigational policies and procedures. The investigational report will be submitted to the DMEC chair.

The DMEC chair will be notified within 24 hours of the research team being notified of all serious adverse events.

All AE and SAE and the clinical and research team actions will be logged in the Trial Management File.

15 Ethics and regulatory approvals

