2.0 Definitions related of safety

- 2.1 Mental health safety symptom severity, deterioration is assessed using the PCL-5 selfreport screening questionnaire completed by the participant at the beginning of every therapy session until discharge. Any existing or emergent safeguarding and or vulnerable adult concern will be assessed and monitored at each session with proportionate action taken in accordance with legislative reporting requirements.
- 2.2 Mental health safety is assessed using the PCL-5 and PHQ-9 (question 9) self-report screening questionnaires completed by the participant at the following time points following FIRST therapy discharge (intervention arm), or while awaiting therapy commencement at 20-weeks (control arm): 6 weeks post randomisation, 12 weeks post randomisation, 20 weeks post randomisation and 52 weeks post randomisation (for those in the intervention arm).
 - 2.2.1 The named researcher will review all incoming follow up PCL-5 and PHQ-9 scores within 72 hrs of receipt.
 - 2.2.2 If PHQ9, Q.9 (risk of self-harm) is scored 1-3 this will trigger a safety contact email correspondence from the assessors (see 4.0).
- 2.3 PTSD Adverse Events are defined as a ≥10 point rise in the self-report PCL-5 since the previous therapy session or a 15 point rise from baseline or the maximum score of 80 being reached and/or relapse into alcohol and/or substance misuse at a hazardous level which integrated with the clinical judgement of the treating therapist will determine the action taken.
- 2.4 The risk of Self-Harm Adverse Event is defined as when the research team has been unable to make contact with the participant (see 4.5) on three separate occasions and contact is made from the research team to the participant's GP.
- 2.5 PTSD Serious Adverse Events are defined as hospital admission for mental ill-health, self-harm, suicide and attempted or completed suicide.

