5.0 Care escalation procedures in the case of adverse event

- 5.1 If at point of referral or during the course of treatment, Inspire therapists become concerned about the welfare of any participant or immediate family member they will escalate their concerns through Inspire's standardised risk assessment, escalation, management and safeguarding policies and procedures. Where necessary they will contact the participant's GP to mobilise referral to crisis response, NHS primary or secondary care. Likewise, if a safeguarding and vulnerable adults concern is identified this will be escalated, acted on and reported to the relevant statutory body safeguarding team.
 - 5.1.1 The PCL- 5 will be completed at each therapy session. If ≥10 point rise in PCL-5 score occurs since the previous therapy session, or 15-point rise from baseline, or the maximum score of 80 is recorded on the PCL-5, they will use their clinical judgement to assess whether escalation is appropriate.
 - 5.1.2 Any ≥10 point rise in PCL-5 score that occurs since the previous therapy session, or 15-point rise from baseline, or the maximum score of 80 recorded on the PCL-5, will be detected by the unblinded member of the research team (investigator [name]) who will inform the DMEC chair within three working days.
- 5.2 If a participant's PCL-5 score rises by ≥10 points from the previous follow up, or 15point rise from baseline, or the maximum score of 80 is recorded on the PCL5, the unblinded researcher (investigator [name]) will make contact with the participant within six hours of noting the rise in score and encourage them to contact their GP and/or their case worker. They will advise the participant that the researcher will need to contact the participant's case worker (or GP if no case worker) to alert them to the rise in PTSD symptoms.

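### The 10-point PCL-5 limb of the adverse-event definition is tied to a therapy session, so it cannot apply to waiting-list participants before week 20, contrary to Appendix 1 item 5.2 and section 8.10.2

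*Protocol*

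**What the plan says.** **Definition.** Section 14.1 gives three PCL-5 limbs for a PTSD adverse event: a 10-or-more "point rise in the self-report PCL-5 since the previous therapy session or a 15 point rise from baseline", or the maximum score of 80. Hazardous relapse into alcohol or substance misuse is a further limb, and the treating therapist's judgement guides the action taken. Appendix 1 item 2.3 repeats this and also measures the 10-point limb "since the previous therapy session or a 15 point rise from baseline".

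**Waiting list.** Sections 8.6 and 8.10.2 start FIRST for this arm 20 weeks after randomisation. Appendix 1 item 2.2 schedules the PCL-5 and PHQ-9 for them at 6, 12 and 20 weeks. Section 8.10.2 says that "any escalation of symptoms in waiting list participants will be detected and recorded as" an adverse event, and cites Appendix 1.

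**Escalation.** Appendix 1 section 5.0 is headed "Care escalation procedures in the case of adverse event". Items 5.1.1 and 5.1.2 deal with therapy sessions. Item 5.2 deals with follow-up and acts when a participant's "PCL-5 score rises by ≥10 points from the previous follow up", on a 15-point rise from baseline, or on a score of 80. The action is contact with the participant and with the case worker or GP.

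**Reporting.** Section 14.3 starts contact with the words "If the participant scores on the PCL-5 indicate an adverse event", and then says "All AE will be recorded and reported to the study PI within 72 hours".

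**The concern.** The definition and the follow-up trigger use different reference points. Before week 20 a WL participant has no previous therapy session, so the 10-point limb has nothing to be measured from. The reference to a treating therapist suggests that the definition was written for people in therapy and was not adapted for the waiting list.

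Two things are at stake. First, section 10.8.1 treats a change of 10 points or more as the minimal clinically important difference. A WL rise of that size between follow-ups can therefore lack AE status, although 8.10.2 promises to record it and 10.7 makes WL safety an object of the internal pilot. Second, AE ascertainment differs by arm. FIRST participants can meet the 10-point limb during therapy, and at follow-up relative to their last session. WL participants cannot meet it before week 20, so AE counts by arm would not rest on the same rule.

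**Working it through.** The protocol states no figure to reproduce. The check compares the rules and then enumerates scores.

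**Rules for a WL participant before week 20**

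| PCL-5 criterion | 14.1 and item 2.3 (AE) | Item 5.2 (contact) |
|---|---|---|
| Rise of 10 or more | from previous therapy session: none exists | from previous follow-up |
| Rise of 15 from baseline | applies | applies |
| Score of 80 | applies | applies |

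So the two rules differ for this group only in the first row.

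**Inputs.** Let b be the baseline score, p the previous follow-up score and y the current score, all integers from 0 to 80 (10.8.1). The 15-point limb is read as 15 or more. The illustrative baseline of 57 is the feasibility-trial mean in section 5.5.

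**Scores that meet 5.2 but no PCL-5 limb of 14.1**

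Conditions: y − p ≥ 10, y − b < 15 and y < 80. Equivalently, p + 10 ≤ y ≤ min(b + 14, 79). The number of such scores is min(b + 4, 69) − p + 1, or zero if that is not positive.

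| b | p | Scores in the gap | Count |
|---|---|---|---|
| 57 | 52 | 62 to 71 | 61 − 52 + 1 = 10 |
| 57 | 57 | 67 to 71 | 61 − 57 + 1 = 5 |
| 57 | 60 | 70 to 71 | 61 − 60 + 1 = 2 |
| 57 | 61 | 71 | 61 − 61 + 1 = 1 |
| 57 | 62 | none | 61 − 62 + 1 = 0 |
| 66 | 66 | 76 to 79 | 69 − 66 + 1 = 4 |
| 70 | 69 | 79 | 69 − 69 + 1 = 1 |
| 70 | 70 | none | 69 − 70 + 1 = 0 |

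At baseline 57 a WL participant meets a PCL-5 limb of 14.1 only from 57 + 15 = 72. For baselines up to 65 the gap exists only if the previous follow-up is at most 4 points above baseline, and it ends at baseline + 14. Above 65 it narrows because the score-80 limb takes over.

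**Worked case.** Baseline 57, week 6 57, week 12 68. The rise from the previous follow-up is 68 − 57 = 11, so 5.2 requires contact. The rise from baseline is also 11, which is below 15, and 68 is below 80, so 14.1 is not met. Section 14.3 makes contact, recording and the 72-hour report depend on AE status and, read literally, requires none of them.

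**Does 5.2 itself confer AE status?** Its heading implies so, but the item contains no recording step. Where Appendix 1 wants registration it says so, as in item 4.5 for unanswered self-harm contacts. Item 5.1.2 sends session-based rises to the chair of the data monitoring and ethics committee (DMEC) within three working days; item 5.2 has no equivalent.

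**The case against.** The strongest reply is that Appendix 1, read as a whole, already settles the intent. Section 5.0 concerns adverse events and splits by setting. Item 5.2 carries the same three thresholds with the reference moved to the previous follow-up, and 8.10.2 points to that appendix. On that reading a WL rise of 10 or more is an AE and only the wording is unaligned. This is a fair account of what was probably intended, and it is why the point is minor. It does not remove the contradiction, because both formal definitions say otherwise and 14.3 depends on them.

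Other safeguards also stand. The 15-point and score-80 limbs cover the waiting list. All follow-up PCL-5 and PHQ-9 scores are reviewed within 72 hours. Safety issues go to the DMEC within 48 hours of each fortnightly meeting, and the DMEC has unmasked access to all data. Question 9 of the PHQ-9 is a separate route for self-harm risk, though it does not record a rise in PTSD symptoms.

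Part of the gap is rebound. With baseline 57 and previous score 52, scores of 62 to 66 are only 5 to 9 points above trial entry, so the clinical-importance argument is weaker there.

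Three stronger readings are tempting and are not supported:

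- A reader might infer that WL deterioration would go unnoticed or unanswered. Item 5.2 and the 72-hour score review say otherwise.
- A reader might infer that the limb also fails for FIRST participants after discharge. They have a last session, with a PCL-5 taken at its start, as reference.
- A reader might infer that different staff would classify the same score differently. Sections 10.5 and 14.3 and item 5.2 point to a single unmasked safety researcher.

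**Conclusion.** The concern holds as an internal contradiction in a safety definition. Before week 20 the 10-point limb of 14.1 and item 2.3 cannot apply to WL participants, whereas 5.2 acts on such a rise at follow-up and 8.10.2 promises to record any escalation. The consequence is confined to AE status, counting and reporting, and to ascertainment that differs by arm; detection and clinical response are preserved if 5.2 is followed.

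The size is exact for any given pair of scores (67 to 71 when baseline and previous follow-up are both 57), but the number of people affected cannot be derived from the protocol. The conclusion rests on reading 14.1 and 14.3 literally and on taking the 15-point limb as 15 or more. Severity: a minor alignment.

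**What to change.** In 14.1 and Appendix 1 item 2.3, change the limb to a rise of 10 or more *since the previous therapy session or previous follow-up*. State whether baseline counts as the previous follow-up at week 6. In item 5.2, state that such a rise is registered as an AE. Narrowing the promise in 8.10.2 would remove the inconsistency too, but it would withdraw a safety commitment and leave the definition unrepaired.

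The change is wording only and needs no new data. Its cost is more AE entries, some from measurement error alone. As an illustration, suppose that nobody truly changes. Assume true scores with mean 57 and between-person SD 12, an independent error at each assessment, scores kept within 0 to 80, and baselines above 32 and below 80. The simulated share of WL participants with any PCL-5-defined AE by week 20 is then:

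| Assumed error SD | Current wording | Fix, follow-ups only | Fix, baseline also counts |
|---|---|---|---|
| 4 | 4% | 13% | 16% |
| 5 | 9% | 24% | 29% |
| 6 | 14% | 34% | 40% |
| 7 | 20% | 44% | 49% |

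These SDs are assumptions, apart from the feasibility mean of 57. Every AE in the table is a false positive by construction, so it shows cost and is no evidence of missed deterioration. It does show that the choice on baseline at week 6 matters. FIRST participants will still have extra PCL-5 assessments at sessions, so AEs found at scheduled follow-ups are best reported separately from those found in sessions.

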8.3.3 Eligibility screening

- 1) Initial self-reported screening via the website.
- 2) Following expression of interest, potential participants will be asked to complete the online PCL-5 scale to screen for the severity and breadth of PTSD symptoms [22] and the AUDIT questionnaire [76] to screen for alcohol dependency. If they score >32 on the PCL-5 and <20 on the AUDIT, potential participants will be asked to complete informed consent by a member of the trial management team and they will be invited for an eligibility confirmation assessment via videocall within two weeks.

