8.6 Planned interventions and delivery

The experimental therapy, FIRST, uses non-propriety, copyright free, techniques with the intellectual property shared between [name] and King's College London. All participants will be randomly allocated to receive FIRST within three weeks of randomisation or to a waiting list group who will receive FIRST 20 weeks following randomisation.

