8.7 Experimental intervention

FIRST is a brief intervention with minimal and non-traumatising exposure to the original stimulus. It is delivered in 3 to 4 x 90-120 minute sessions by a FIRST therapist via videocall. FIRST rewrites the emotional elements of the memory. FIRST therapy will be delivered over a minimum of three days and a maximum of four weeks. The two factors determining this are a) there must be one sleep cycle between each therapy session and b) scheduling of therapy sessions for the participant and the therapist. The evidence to date indicates that therapy should be completed within four weeks. The FIRST protocol incorporates 18 steps in five stages (table 3). Participants will be asked at all data collection timepoints if they have undertaken any additional therapy for other mental health symptoms such as mood or anxiety, as well as any additional therapy for PTSD.

Stage	Clinical technique	Theory/evidence for the technique
Pre- randomisation assessment by DES [77]	The potential participant is assessed to determine their ability to manage their own association and dissociation processes for suitability of the FIRST protocol.	Participants scoring <31 on the DES-11 proceed as per therapy protocol. Go point 1. Participants scoring between 32-42 (referred to as High DES-11 in following text) proceed with therapist treating them as if the client has complex PTSD and an active dissociation mechanism and modifies therapeutic protocol. GO point 1. Participants with DES-11 score ≥43 should have been excluded prior to randomisation. STOP point
i). Priming process	Prior to commencing work with a trauma memory, the client is primed to the process by completing a full run through of the key elements of the protocol on a neutral memory experience.	 Associational learning provides the opportunity during the priming process to strengthen prefrontal cortex synapses required for memory reconsolidation and alteration in decision making processes [66]. NLP trauma therapy techniques use priming processes before the client engages with the trauma story [21, 29, 78]. If the client has a high DES-11 score at assessment, the protocol follows a revised 'neutral activity double dissociation' visual format at this point. If the client can manage this they proceed into the protocol treatment. – GO point 2. If the client cannot follow the revised visual format

Table 3. The FIRST Protocol and therapeutic Stop/Go points

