10.5 Randomisation and stratification

King's College London Clinical Trials Unit (KCTU) will provide a computer randomisation service. Stratification will be undertaken on diagnosis of PTSD or CPTSD, age and sex. Randomisation will take place after the eligibility confirmation assessment and once baseline data has been completed. Participants will be randomised to the intervention arm where they will receive therapy immediately or to the waiting list control.

Only three members of the research team will be unmasked: the lead clinical provider, the safety monitoring researcher and the trial statistician (the senior statistician will remain masked). All those entering data will be masked to treatment group. For participants randomised to the intervention group, therapy will commence within three weeks. If participant holidays are arranged, randomisation will be delayed ensuring this timeline can be maintained.

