14.2 Serious adverse events

PTSD Serious Adverse Events are defined as hospital admission for mental ill-health, self-harm, suicide and attempted or completed suicide.

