3.0 Safety net procedures for between therapy and follow up time points

- 3.1 All participants will be offered a *Contact Card* at the point of randomisation. This will list the contact details of services to call 24/7 if they feel they need to talk with someone about their mental health outside of their therapy session and throughout their trial participation. Contact details will include Lifeline, Samaritans and their GP and where appropriate their Aftercare case worker and Inspire's 24/7 helpline.
 - 3.1.1 For participants in therapy, the therapist will record participant self-reports of all contacts being made in the therapy safety log.
 - 3.1.2 For participants in follow up, the researcher will note such self-reports in the data collected and ask the participant for details. Details, if provided, will be recorded in the researcher's participant safety log.
 - 3.1.3 The unblinded researcher will review the therapy database weekly to determine if any activity has been logged in the previous seven days.

4.0 Care escalation procedures in the event of a risk of self-harm reported on the PHQ-9

- 4.1 If the participant self-reports thoughts of self-harm on the PHQ-9, by answering 1-3 on question 9, the safety contact communication will be triggered.
- 4.2 On identifying a score of 1-3 on Q9, the research team assessor will contact the participant to ask them about their response and to suggest they may wish to speak to their GP for support.
- 4.3 If the research team assessor is unable to make contact or do not hear back from the participant within 24 hours, they will send a follow-up email.

- 4.4 If research team assessor still receive no response, they will send a third communication saying they have emailed the participant twice over the past two days and if they do not hear from them within 24 hours they will get in touch with their GP to let them know that they are concerned about them.
- 4.5 If this final communication does not elicit a response, the research team assessor will escalate the reporting and contact the GP, to voice our concerns. This will be reported to one of the study's senior investigators ([name] or [name]) and be registered as an adverse event.

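### Alcohol or substance relapse and the serious adverse events have no direct follow-up question in either arm, and only FIRST has therapist contact before week 20, so harm counts by arm may not be like for like

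*Protocol*

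**What the plan says.** **Defined harms.** Section 14.1 (repeated in Appendix 1, item 2.3) counts certain PCL-5 rises as adverse events and adds "relapse into alcohol and/or substance misuse at a hazardous level which integrated with the clinical judgement of the treating therapist" will determine the action. Section 14.2 states: "PTSD Serious Adverse Events are defined as hospital admission for mental ill-health, self-harm, suicide and attempted or completed suicide".

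**Scheduled measurement.** Section 8.3.3 uses "the AUDIT questionnaire [76] to screen for alcohol dependency", and a score below 20 is needed to proceed. AUDIT does not appear again in Table 7. For safety outside therapy, Appendix 1 item 2.2 names the PCL-5 and PHQ-9 question 9 at 6, 12 and 20 weeks in both arms, and at 52 weeks in FIRST only. Section 8.7 adds a question about additional therapy at every data collection point.

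**Therapist contact.** Section 10.5: "For participants randomised to the intervention group, therapy will commence within three weeks". Section 8.7: "FIRST therapy will be delivered over a minimum of three days and a maximum of four weeks", in 3 to 4 sessions of 90-120 minutes. The comparison is "to a waiting list group who will receive FIRST 20 weeks following randomisation" (section 8.6). While a participant is in therapy, "the therapist will record participant self-reports of all contacts being made in the therapy safety log" (Appendix 1, item 3.1.1), and an unblinded researcher reviews the therapy database weekly (item 3.1.3).

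**Waiting list.** Section 8.10.2 says that "any escalation of symptoms in waiting list participants will be detected and recorded as" an adverse event.

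**Use.** Under section 12.4 the DMEC assesses safety with unmasked access to all data. Section 10.7 makes WL safety an object of the internal pilot.

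**The concern.** A between-arm comparison of harm needs each event to be looked for in the same way in both arms. Here several defined harms have no scheduled question of their own, and one arm has additional clinical contact during which such events can come up. If more is found in FIRST simply because someone is there to hear it, FIRST may look more harmful than it is, or the 20-week wait may look safer than it is. Relapse is a realistic event, since people with AUDIT scores up to 19 can enter. A later analysis plan cannot repair this, because data not collected cannot be recovered at analysis.

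**Working it through.** There is no stated figure to reproduce, so the check counts what the protocol schedules in each arm from randomisation to week 20.

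**1. Scheduled checks after baseline** (Table 7; section 8.7; Appendix 1, items 2.1-2.2)

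| Check | FIRST | WL |
|---|---|---|
| PCL-5 | 3 follow-ups + 3 to 4 sessions = 6 to 7 | 3 |
| PHQ-9 item 9 | 3 | 3 |
| Alcohol or substance use | 0 | 0 |
| Direct question on admission, self-harm or suicide attempt | 0 stated | 0 stated |
| Therapist sessions | 3 to 4 | 0 |

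Therapist time in FIRST runs from 3 x 90 min = 4.5 h to 4 x 120 min = 8 h.

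**2. Length of the imbalance.** Therapy starts by week 3 and lasts at most 4 weeks, so it ends by week 3 + 4 = 7. For at least 20 - 7 = 13 weeks the two arms have the same research-team surveillance.

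**3. What the common routes capture** (Appendix 1)
- PHQ-9 item 9 scored 1-3: an assessor contacts the participant, with escalation to the GP if there is no reply (items 4.1-4.5). This detects thoughts of self-harm.
- PCL-5 rise at follow-up: the unblinded researcher contacts the participant (item 5.2). This detects symptom change.
- Crisis-service contacts that a participant reports: the researcher records them and asks for details (item 3.1.2). This detects help-seeking.

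Each can lead to a conversation in which an admission or attempt emerges. None measures the event itself. Someone admitted between timepoints who scores 0 on item 9, has no qualifying PCL-5 change and mentions no crisis contact triggers nothing. None of the routes concerns alcohol or substance use.

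**4. SAE handling.** Section 14.3 and Appendix 1 section 6 set out investigation for events during therapy and after discharge from the therapy provider. A WL participant before week 20 fits neither description, although the DMEC chair is told of every SAE the team learns of (item 6.3).

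**5. Illustration on assumed detection rates.** Suppose the true risk is equal, events are spread evenly, 90% are detected while a therapist is involved, and a proportion d is detected otherwise. Let w be the therapist share of the 20 weeks, at most 7/20 = 0.35. The apparent FIRST:WL ratio is [0.9w + (1 - w)d] / d. With w = 0.35:
- d = 0.9: (0.315 + 0.585) / 0.9 = 1.00
- d = 0.5: (0.315 + 0.325) / 0.5 = 1.28
- d = 0.3: (0.315 + 0.195) / 0.3 = 1.70

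A shorter course of therapy moves the ratio towards 1. The protocol supports no choice of d, nor the 90%.

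**The case against.** The strongest reply is that both arms share a working safety system. PHQ-9 item 9 and the PCL-5 go to everyone at 6, 12 and 20 weeks, scores are reviewed within 72 hours, and a trigger leads to direct contact. Section 14.3 requires all AEs and SAEs to be logged. Table 7 lists questionnaires and tasks, so it need not show adverse event forms. In section 14.1 the therapist's judgement governs the response to relapse and not its detection, and no passage schedules therapist questions on drinking, admission or attempts. The Appendix 2 flow diagram and the end of the self-harm sentence in 14.1 are not readable in the available text.

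Much of this stands, and it rules out several stronger readings that a reader might infer:
- That serious events can be found only through a therapist, or that nobody asks WL participants anything before week 20. The shared routes show otherwise.
- That section 8.10.2 is contradicted. It promises detection of symptom escalation, which the PCL-5 and PHQ-9 do measure; it says nothing about admissions or substance use.
- That a particular inflation of harm in FIRST can be stated. Better detection by therapists is plausible but not documented, and it would apply for about 7 of the 20 weeks at most.

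The reply leaves two things unanswered. A duty to log an event does not create a means of learning of it, and relapse has no stated follow-up route in either arm beyond what may emerge in therapy.

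**Conclusion.** The point holds as a gap in ascertainment. After screening, the protocol states no direct enquiry about alcohol or substance relapse, mental-health admission, self-harm or suicide attempt in either arm. For the serious events there are indirect routes common to both arms; for relapse there are none. The extra therapist sessions and weekly-reviewed database in FIRST, up to about week 7, mean that counts by arm may not be like for like and that some WL events may be missed. The size is unknown: on the assumed rates above the apparent ratio runs from 1.00 to 1.70, and none of these values is an estimate. The conclusion assumes that no adverse event form with these questions exists in the parts of the protocol that could not be read. The primary PCL-5 comparison is not affected. The gap deserves correction because the DMEC will read these counts by arm and the remedy is small.

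**What to change.** Add a short, identical set of yes/no items to the existing Qualtrics survey at 6, 12 and 20 weeks in both arms, and at 52 weeks in FIRST. The items should ask, since the last assessment, about mental-health hospital admission, self-harm, suicide attempt, and hazardous alcohol or substance relapse. Add a row to Table 7 and name the items in sections 14.1 and 14.2 as the source for these events. Base the between-arm safety comparison to week 20 on this source, and list therapist-reported events separately. Reconcile section 14.3 and Appendix 1 section 6 so that it is clear which passage covers a WL participant before therapy.

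The cost is a minute or two per timepoint, on a battery that section 10.2 already calls burdensome, and more events to review. Repeating the full AUDIT is optional and need not be part of the change. The items still depend on a returned survey, and section 10.6 allows for 20% loss by week 20, so they equalise the enquiry without guaranteeing complete capture.
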